3.11.1. Statistical Justification

Assuming the pooled response rate of 40% is met, the probability of incorrectly declaring futility with 15 evaluable patients is 0.0905. This is calculated using the binomial cumulative distribution function with parameters $n=15$, $p=0.4$, $x=3$.

The single stratum futility assessment allows for the possibility that response rates in a single stratum may be lower than 40%, but the pooled response rate after incorporating the other strata could still reach 40%. The per-stratum futility threshold is intended to terminate enrollment in a stratum where the true response rate can be expected to be $<25\%$. Under a binomial distribution with parameters $n=8$ and $p=0.25$, the probability of observing $x=0$ successes is 0.10011.

4. STUDY ANALYSES

4.1. Study Population Analyses

4.1.1. Patient Disposition

The number of screened patients, proportion of screened patients enrolled, and reasons for screen failure will be summarized by transfusion history group at screening. Proportions will be out of the total number of patients screened.

Patient disposition will be tabulated by stratum and overall for all enrolled patients. Summaries will include:

- Patients enrolled
- Patients dosed
- Patients in each analysis population
- Patients who completed the primary treatment period (through Week 24 study visit)
- Patients who completed the extension treatment period (through Week 48 study visit)
- Patient's treatment discontinuations and primary reasons(based on End of Treatment form) by treatment period
- Patient's study discontinuations and primary reasons(based on End of Study form) by treatment period

Patients who discontinued treatment/study due to the current early study termination will have the corresponding primary reason reported as "Study termination by sponsor".

A by-patient data listing will be included.

4.1.2. Demographics and Baseline Characteristics

Demographics and baseline characteristics will be summarized and presented by transfusion history stratum and overall in FAS. Age, age group (<64, 65-74, ≥ 75), gender, ethnicity, race, height, weight, and body mass index (BMI) at the screening visit will be summarized using descriptive statistics by transfusion history stratum and overall.

Demographic and baseline data for each patient will be provided in data listings.

4.1.3. Prior and Concomitant Medications

Prior and concomitant medications will be coded according to the March 2022 version of the World Health Organization (WHO) Drug Global dictionary (B3 format). Prior medications and non-medication therapies will be reported only in data listings.

Concomitant medications are defined as medications started prior to or after the start of study treatment and continued during the study or until the completion of the End of Study (EOS) visit. Prior medications are defined as those that both start and end before dosing.

Concomitant medications will be summarized descriptively for each stratum and overall by therapeutic subgroup (Anatomical Therapeutic Chemical [ATC] 2nd level), chemical subgroup (ATC 4th level) and preferred name for the FAS and displayed in data listings. Patients taking the same medication multiple times will be counted once per medication.

Concomitant procedures (non-medical therapies) will be coded using version 26.1 of the Medical Dictionary of Regulatory Activities (MedDRA). Concomitant procedures will be reported only in data listings.

4.1.4. Protocol Deviations

Major protocol deviations will be summarized in FAS with descriptive statistics for each transfusion history stratum and overall by type (as applicable). All protocol deviations will be presented in a data listing.

4.1.5. Medical and Disease Histories

4.1.5.1. MDS Disease History

Patient MDS disease history will be summarized in FAS by transfusion history stratum and overall with descriptive statistics for years since diagnosis, ECOG performance status at W1D1 (0, 1, 2), and IPSS-R classification at Screening (Very Low, Low, Intermediate).

4.1.6. Prior and Concomitant MDS Treatment

Prior and concomitant treatment for the following supportive therapies will be presented in a data listing: any iron chelation therapy, any erythropoiesis-stimulating agent, G-CSF, luspatercept, lenalidomide.

Prior and concomitant systemic therapy will be presented in a data listing by therapy type (systemic cytotoxic chemotherapy, systemic targeted therapy, hypomethylating agent, anti-cancer hormonal therapy, immuno-oncology agents, other systemic therapy).

4.1.6.1. Transfusion History

By-patient data listings for RBC and platelet transfusion prior to initiation of study treatment will be presented.

4.1.6.2. General Medical History

Medical history will be coded using version 26.1 of MedDRA. Number and percentage of patients who had medical history will be tabulated in FAS by transfusion history stratum and overall using system organ class (SOC) and preferred term (PT). Patients will be counted only once within each SOC and PT.

By-patient data listings will be presented.

4.2. Efficacy Evaluation

Efficacy analyses will be conducted using the EES.

4.2.1. Analysis of Primary Endpoints

4.2.1.1. HI-E Response and MDS assessments

The proportion of patients with HI-E response ≥ 8 weeks within 24 weeks of etavopivat treatment will be analyzed across the pooled strata and within each stratum. Patients will be considered responders if they satisfy HI-E criteria during any continuous ≥ 8 -week treatment interval up to W24D1.

HI-E criteria are defined based on the patient's transfusion history stratum at D1:

NTD: A patient is considered a responder where at least one continuous interval ≥ 8 weeks occurs where all of the following criteria are met:

- Hb is increased by ≥ 1.5 g/dL relative to baseline at 2 or more consecutive visits
- Relapse date (date of first Hb measurement with < 1.5 g/dL change from baseline following the qualifying increase) occurs at least 8-weeks after the first incidence of qualifying Hb increase
- Patient is free of RBC transfusions

LTB: A patient is considered a responder if they are free of RBC transfusions over any continuous 8-week period.

HTB: A patient is considered a responder if they have a $\geq 50\%$ reduction in RBC transfusion burden relative to baseline RBC transfusion burden per 8 weeks over any continuous 8-week period.

Percent reduction in RBC transfusion burden is calculated for all rolling 56-day intervals in the 24-week primary treatment period (i.e. Days 2-57, Days 3-58,..., Days 113-168) as

$$-100 \times \frac{RBC \text{ units transfused in 56 day interval} - \text{Baseline RBC transfusion burden per 8 weeks}}{\text{Baseline RBC transfusion burden per 8 weeks}}$$

The numerator for the response rate will be the total number of responders (summed across all baseline transfusion categories). The denominator will be the number of patients in the EES.

MDS baseline assessment including the score based on Revised International Prognostic Scoring System (IPSS-R) for MDS and MDS response assessment will be presented in data listings.

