6.7 Concomitant Therapy

6.7.1 Concomitant Medications

All medications taken by patients from Screening until the completion of the Safety Follow-up visit will be documented as concomitant medications. The reported medications will be reviewed and evaluated by the Investigator to determine if they affect a patient's eligibility or continued participation in the study.

Patients are required to avoid starting new non-prescription medicine within 14 days to first study dose and throughout the study, unless discussed with the investigator. The use of St John's wort should be avoided in this period.

Strong inducers of CYP3A4/5 (see Appendix F) are prohibited during the study.

With the exception of strong inducers of CYP3A4/5, concomitant prescribed medications are allowed for patients if prescribed by the Investigator to treat clinical events or exempted by the Medical Lead on a case-by-case basis because they would be unlikely to affect the study results or patient safety.

Use of erythropoietin or thrombopoietin mimetics are prohibited during the study and within 30 days prior to starting study treatment, with the exception of erythropoietin (ESA) in patients with diagnosed stage 3 or 4 CKD and who had been on a stable ESA dose for ≥6 months and plans to continue ESA at the same dose throughout the duration of the study. Hematopoietic growth factors for the treatment of transient neutropenia may be used when clinically indicated.

Current use of luspatercept is prohibited during the study and within 30 to 80 days before starting study treatment (based on transfusion history).

40 of 77

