3. GENERAL STATISTICAL METHODS

3.1. Sample Size Justification

An overall sample size of N=45 will provide 87.3% power to detect an increase in the response rate for the HI-E criteria. Specifically, the assumed response rates are 40% for the etavopivat intervention and 20% otherwise (null-hypothesis comparator). One-sided testing, a significance level of 0.025, and the exact binomial distribution are used for the calculations.

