5.2. Changes to Planned Analyses

For the purpose to support an abbreviated CSR, a selected set of endpoints are included in this SAP. The following analysis populations and endpoints mentioned in the protocol are not included:

Protocol Section 3.2:

- The HI-E for \geq 8 weeks within 16 and 48 weeks of etavopivat
- The HI-E for \geq 16 weeks within 24 and 48 weeks of etavopivat
- Overall response rate (2006 International Working Group [IWG] Criteria) (see protocol Appendix A)
- Duration of response (2006 IWG Criteria)
- Increase in neutrophils and/or platelets counts
- Decrease in ferritin and transferrin saturation (TSAT)
- Decrease in iron chelation therapy
- Overall survival

Protocol Section 3.3:

- PK: maximum observed plasma concentration, time to maximum observed plasma concentration, area under the plasma concentration-time curve from time zero until the last quantifiable time point (AUC0-last), from time zero to infinity (AUC0-inf), for a dosing interval (AUCtau/AUC0-24).
- RBC 2,3-DPG and ATP levels over time

Protocol Section 3.4:

- Change from baseline in Patient-Reported Outcome Measurement Information System (PROMIS) Fatigue Scale at Weeks 16, 24, and 48
- Change from baseline in The Quality of Life in Myelodysplasia Scale (QUALMS) patient-reported outcome assessment at Weeks 16, 24, and 48
- Cell colony analysis of bone marrow progenitors
- Cytomorphology (blast, M/E, and ringed sideroblast determination) and cytogenetics of bone marrow
- Markers of ineffective erythropoiesis and iron metabolism
- Cancer-associated mutations and/or genetic alterations in responding and non-responding patients
- Flow cytometry analysis of terminal erythroid differentiation

Protocol Section 9.2:

- Interim Assessment Set and Per-Protocol Set

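### The primary responder rule has no condition on other anemia or MDS therapy, so a response after such a therapy starts is counted as an etavopivat response

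*SAP*

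**What the plan says.** **The rule.** SAP 4.2.1.1: "Patients will be considered responders if they satisfy HI-E criteria during any continuous" treatment interval of 8 weeks or more up to W24D1. The NTD criteria are the hemoglobin gain, its persistence, and "Patient is free of RBC transfusions". LTB patients must be free of red-cell transfusion for 8 weeks. HTB patients must have at least a 50% reduction in units over 8 weeks. The denominator is the Efficacy Evaluable Set (EES).

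**The other therapies.** Protocol 6.7.1 prohibits erythropoietin and thrombopoietin mimetics on study, except a stable ESA dose in stage 3 or 4 CKD, and states "Current use of luspatercept is prohibited during the study". It does not name lenalidomide or hypomethylating agents. Those appear only at entry: exclusion 19 (prior azacitidine or decitabine) and exclusion 20 (recent use of, or anticipated need for, lenalidomide among other agents).

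**What is reported.** SAP 4.1.3 summarizes concomitant medications and SAP 4.1.4 summarizes major deviations. SAP 4.1.6 puts prior and concomitant use of "any iron chelation therapy, any erythropoiesis-stimulating agent, G-CSF, luspatercept, lenalidomide" in a listing, and lists systemic therapy by type, including hypomethylating agents.

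**The sensitivity set.** Protocol 9.6 planned a sensitivity analysis in the Per-Protocol Set (PPS). SAP 5.2 names "Interim Assessment Set and Per-Protocol Set" among the items not included.

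**The concern.** The trial has one arm, and protocol 9.6.1 compares its response rate with a fixed 20%. No control group would absorb the effect of other treatment. If a patient starts an ESA or luspatercept in the first months, stays on etavopivat, and then becomes transfusion-free or gains 1.5 g/dL, the rule as written gives the response to etavopivat. The error runs one way: counting such windows can turn a non-responder into a responder, never the reverse. With the PPS gone, no planned analysis shows what the rate would be without these patients.

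**Working it through.** **Step 1. Does any provision close a window?**

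| Place | What it conditions on | Other anemia or MDS therapy |
|---|---|---|
| SAP 4.2.1.1, NTD | Hb gain, persistence, no RBC transfusion | silent |
| SAP 4.2.1.1, LTB | no RBC transfusion | silent |
| SAP 4.2.1.1, HTB | RBC units | silent |
| Protocol 9.6.1 | same three conditions, less explicit for NTD | silent |
| SAP 2.1, EES | Week 24 visit done, baseline present | silent |
| SAP 3.9, missing data | dates and missing values | silent |

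The result follows from silence: the algorithm, run as written, counts the window.

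**Step 2. How much of the period is open?** SAP 4.2.1.1 evaluates HTB patients over rolling 56-day intervals from Days 2-57 to Days 113-168. The last holds 168 − 113 + 1 = 56 days. A therapy started by Day 112 (16 × 7) therefore leaves at least one full window after it. A later start can still help complete a window that began earlier.

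**Step 3. Size per case.** Each such responder adds 1/N.
- N = 45 (planned): 1/45 = 2.2 percentage points.
- N = 20 (assumed, because the study ended early and the final number is not given): 1/20 = 5 points.

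**Step 4. The plan's test, to scale the effect.** SAP 3.1 states: "An overall sample size of N=45 will provide 87.3% power to detect an increase in the response rate for the HI-E criteria"; "the assumed response rates are 40% for the etavopivat intervention and 20% otherwise"; "One-sided testing, a significance level of 0.025, and the exact binomial distribution are used for the calculations".
- The smallest r with P(X ≥ r | 45, 0.20) ≤ 0.025 is r = 15, with one-sided error 0.02499.
- Exact power is P(X ≥ 15 | 45, 0.40) = 85.7%, which is 1.6 points below the stated 87.3%.
- The normal approximation gives Φ[(0.20√45 − 1.96 × 0.40)/√0.24] = 87.25%, closer to the stated figure. The gap does not affect this point.

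**Step 5. Sensitivity, on assumptions.** Let m of 45 patients start such a therapy and respond with probability q, while the rest respond at 20%. The number of responders is the sum of Binomial(45 − m, 0.20) and Binomial(m, q). The three middle columns give the chance of 15 or more responders when the windows count. The last two show the proposed rule at its worst, where none of the m had completed a window earlier and all become non-responders.

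| m | q = 0.4 | q = 0.6 | q = 1 | Error under the rule | Power under the rule |
|---|---|---|---|---|---|
| 0 | 0.025 | 0.025 | 0.025 | 0.025 | 85.7% |
| 1 | 0.030 | 0.034 | 0.044 | 0.020 | 83.0% |
| 2 | 0.035 | 0.046 | 0.073 | 0.016 | 79.9% |
| 3 | 0.041 | 0.062 | 0.118 | 0.013 | 76.4% |

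If the other drug adds nothing (q = 0.2), the error stays at 0.025. Neither m nor q is in the documents. The table shows sensitivity at the planned size and does not forecast this study.

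**The case against.** The strongest reply is that the path to a miscount is narrow.
- Inclusion 8 requires that luspatercept has failed, was not tolerated, or is contraindicated or not indicated. Inclusion 6 sets a similar condition for ESAs when erythropoietin is 200 U/L or lower. Inclusion 9 requires that no suitable alternative exists.
- Exclusion 20 removes patients with an anticipated need for ESAs, other growth factors or lenalidomide.
- Protocol 7.2.1 makes noncompliance and lack of efficacy reasons to stop treatment, and a patient who stops before the Week 24 visit leaves the EES.

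A miscounted patient must start the drug by about Week 16 (or start later and use it to complete a window already begun), stay on etavopivat, complete Week 24, have no earlier window, and then respond. All of this stands as a reason to expect few cases. It does not close the gap. Patients with erythropoietin above 200 U/L need not have failed an ESA, and no section says that starting another therapy ends a window or removes a patient who reaches Week 24.

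A reader might infer four stronger points that the documents do not support:
- *The SAP expects prohibited use.* SAP 4.1.6 covers prior use, which eligibility makes likely, as well as permitted use such as stable ESA in CKD or growth factors for transient neutropenia.
- *Use would be visible only in a listing.* SAP 4.1.3 and 4.1.4 also summarize medications and major deviations. What is missing is the link to response.
- *The PPS would have removed these patients.* It excluded only major violations that affect efficacy (protocol 9.2), and classification follows a guidance plan (SAP 2.2) that is not among the documents. The removal is also declared openly, for an abbreviated report.
- *All four therapies are prohibited on study.* Protocol 6.7.1 names only ESAs and luspatercept among them.

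**Conclusion.** The gap is real and modest. As written, SAP 4.2.1.1 credits etavopivat with a response that follows another anemia or MDS therapy, and nothing planned separates such responders from the rest. Any such case biases the rate upward by 1/N: 2.2 points at N=45, 5 points at the assumed N=20. The number of cases is unknown and probably small, so the documents do not show that the primary rate is materially inflated.

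The error probabilities in the table depend on assumed m and q and on a 45-patient test. The study stopped early, and SAP 4.2.1.1 itself names no hypothesis test. The per-case shift in the reported rate is therefore the relevant size.

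**What to change.** Add to SAP 4.2.1.1 that only windows completed before the first on-study dose of a confounding anemia or MDS therapy qualify, and name the therapies: ESA start or dose increase outside the permitted stable-dose CKD exception, luspatercept, lenalidomide, and hypomethylating agents. Use the word *confounding* rather than *prohibited*, because protocol 6.7.1 does not prohibit the last two on study. State that responses completed earlier stand, and that patients in the EES with no earlier window stay in the denominator as non-responders.

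This is an analysis rule and changes no patient's management. It costs a short addition to the SAP and some programming. The therapy data are already planned for collection, and SAP 3.9 has a rule for partial start dates of concomitant medications. The downside is that the response rate may be slightly lower. If all affected patients had no earlier window, the table's last columns bound the loss at the planned size: for two patients, power falls from 85.7% to 79.9%.

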3.0 STUDY OBJECTIVES AND ENDPOINTS

3.1 Primary Objective and Endpoints

Objective	Endpoints
To assess hematologic improvement based on an erythroid response (HI-E) for ≥ 8 weeks duration in patients with MDS within 24 weeks of etavopivat treatment	 The HI-E for ≥ 8 weeks within 24 weeks of etavopivat This endpoint will be based on the combined incidence of: Non-transfusion dependent (NTD) patients: ≥ 1.5 g/dL increase in Hb from baseline maintained ≥ 8 consecutive weeks and no transfusion of RBC units for anemia over a continuous 8-week treatment period Low transfusion burden (LTB) patients: absence of any transfusion for ≥ 8 consecutive weeks High transfusion burden (HTB) patients: reduction by ≥ 50% of red blood cell (RBC) units for ≥ 8 consecutive weeks

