5.1 Inclusion Criteria

Participants are eligible to be included in the study only if all the following criteria apply:

Informed Consent

1. Patient has provided documented informed consent; the informed consent form (ICF) must be reviewed and signed by each patient prior to any study-related assessments/procedures being conducted.

Age

2. Age \geq 18 years at time of first dose

Sex and Contraceptive/Barrier Requirements

3. Patients, if female and of childbearing potential, must agree to use acceptable methods of contraception and agree not to donate ova from study start to 90 days after the last dose of study drug, and who if male are willing to use acceptable methods of contraception and agree not to donate sperm, from study start to 90 days after the last dose of study drug.

Disease Specific Requirements

- 4. Documented diagnosis of idiopathic/de novo MDS according to 2016 WHO classification (see Appendix C) that meets IPSS-R classification (see Appendix B) of very low, low, or intermediate risk disease, and:
 - < 5% blasts and no Auer rods in bone marrow based on local pathology review
 - < Intermediate risk cytogenetic abnormalities per IPSS-R
- 5. Anemia defined as:
 - NTD: Subjects with mean Hb concentration < 10.0 g/dL on 2 measurements (1 performed within 3 days prior to W1D1 and the other performed 7 to 28 days prior to W1D1, not influenced by RBC transfusion within 7 days of measurement) and < 3 RBC transfusions for anemia in the prior 16 weeks before W1D1 of etavopivat dosing

OR

- Transfusion Dependent: Subjects having received ≥ 3 units of RBCs for the treatment of anemia within 16 weeks prior to W1D1
- 6. Serum erythropoietin level > 200 U/L, OR, if \leq 200 U/L, subject is non-responsive, refractory, or intolerant to erythropoiesis-stimulating agents, or erythropoiesis-stimulating agents are contraindicated or unavailable.
- 7. Eastern Cooperative Oncology Group performance status of ≤ 2 (see Appendix D)

- 8. Subject is non-responsive, refractory, or intolerant to luspatercept, or luspatercept is contraindicated or not indicated.
- 9. No alternative treatment options are available and/or appropriate for the subject, at the discretion of the investigator.
- 10. Patient is willing and able to adhere to the study visit schedule and other protocol requirements

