(HI-E)		of 2 Hb measurements (apart from any transfusion) within 16 wk before			
		treatment onset			
	Low transfusion	Absence of any transfusions for at least 8 wk in an observation period of			
	burden (LTB)	16-24 wk with the same transfusion policy (defined below) compared with			
		16 wk prior to treatment			
	High	Major response: Transfusion independence, defined by the absence of any			
	transfusion	transfusions over a period of minimum 8 wk in an observation period of			
	burden (HTB)	16-24 wk with the same transfusion policy (defined below) compared with			
		16 wk prior to treatment			
		Minor response: Reduction by at least 50% of RBCs over a minimum of			
		16 wk with the same transfusion policy (defined below) compared with 16 wk			
		prior to treatment			
	On-treatment	Transfusion policy for the individual patient prior to therapy should be			
	RBC	maintained on treatment if not otherwise clinically indicated (documentation			
	transfusion	by the treating physician required); maximum variation between pre- and on-			
	policy	study practice of 1 g/dL (or 0.6 mmol/L) in terms of transfusion threshold			
-	se (pretreatment,	• Absolute increase of $30 \times 10^9/L$ for patients starting with $>20 \times 10^9/L$			
$<100 \times 109/L)$, HI-P	PLTs or			
		• Increase from $<20 \times 10^9/L$ to $>20 \times 10^9/L$ and by at least 100% In addition,			
		Evolution of bleeding symptoms is to be taken into account			
Neutrophil resp	nonse	At least 100% increase and an absolute increase >0.5 × 10 ⁹ /L			
	all patients), HI-N	(pretreatment, $<1.0 \times 10^9/L$)			
	relapse after HI				
l rogression or	reapse area in	For HI-N and HI-P:			
		At least 50% decrement from maximum response levels in			
		neutrophils or platelets, and not meet response criteria when			
		compared to baseline			
		For HI-E:			
		• Reduction in Hb by ≥ 1.5 g/dL, and not meet response criteria when			
		compared to baseline			
		Transfusion dependence			
		HTB: increase in transfusion burden by at least 50%			

Hb = hemoglobin; HI = hematologic improvement; PLTs = platelets; wk = week(s).

^{*}If patients received 1 or 2 RBC concentrates during the 16-wk pre-treatment period, it is recommended that HI-E achievement requires not only transfusion independence but also an increase of Hb by at least 1.5 g/dL (= 0.9 mmol/L).

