3.3. Baseline Definitions

Baseline values for Hb will be defined as the mean of the screening and Day 1 pre-treatment values. If one of the two assessments is missing, then a single assessment prior to the start of study treatment will be defined as baseline.

History of RBC transfusions will be gathered for each patient for up to 16 weeks before start of study treatment. Baseline RBC transfusion burden units per 8 weeks will be defined as the summed units transfused in the 8 weeks up to pre-dose Day 1 (Rel Day -55 to 1).

For all other analyses, baseline will be defined as the most recent non-missing measurement prior to the first administration of study drug.

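### The SAP's NTD response rule lets Hb raised by a transfusion given just before the qualifying interval count toward HI-E response

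*SAP*

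**What the plan says.** SAP 4.2.1.1 scores an NTD patient as a responder when "at least one continuous interval ≥ 8 weeks occurs where all of the following criteria are met". There are three criteria:

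- Size of the rise: "Hb is increased by ≥ 1.5 g/dL relative to baseline at 2 or more consecutive visits".
- Durability, counted from the first qualifying value: "Relapse date (date of first Hb measurement with < 1.5 g/dL change from baseline following the qualifying increase) occurs at least 8-weeks after" that value.
- Transfusion status: "Patient is free of RBC transfusions".

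The third criterion belongs to the interval, and the second shows that the clock starts at the first qualifying Hb. The protocol endpoint (section 3.1) has the same reach: "no transfusion of RBC units for anemia over a continuous 8-week treatment period". The NTD line in protocol 9.6.1 names no transfusion condition.

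The protocol guards Hb against transfusion before treatment only. Inclusion criterion 5 requires entry values "not influenced by RBC transfusion within 7 days of measurement". Appendix A uses as its reference the smallest average "of 2 Hb measurements (apart from any transfusion) within 16 wk before" the start of therapy. SAP 3.3 does not carry even that over: "Baseline values for Hb will be defined as the mean of the screening and Day 1 pre-treatment values". The individual transfusion plan in protocol 8.2.2.1 covers the low- and high-burden strata, not NTD. The SAP's rules for missing data (3.9) and visit windows (3.10) do not deal with Hb after a transfusion.

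**The concern.** A transfusion raises Hb for weeks whether or not the drug works. If it falls shortly before a visit, donor cells can carry the measured value past +1.5 g/dL. The interval then opens at that visit, and the transfusion lies outside it. As long as no further transfusion is given and no measured Hb drops below the threshold for 8 weeks, the patient counts as a responder.

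The error can only add responders, and the study is single-arm with a fixed 20% reference rate in the protocol. Each misclassified patient adds 1/45 = 2.2 percentage points to the pooled rate at the planned size. With 15 patients, the size of the futility look, it adds 1/15 = 6.7 points, and that rule turns on 3 versus 4 responders. The study ended early (SAP 1.1), so the denominator may well be below 45.

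**Working it through.** **1. What the visit schedule demands.** SAP Table 3 puts W10, W12, W14, W16, W20, W22 and W24 on target Days 64, 78, 92, 106, 134, 148 and 162; there is no W18 visit. If all visits are attended, an interval opening at W2-W10, W14 or W16 needs Hb at or above +1.5 g/dL documented over 42 days (3 or 4 visits). One opening at W12 needs only W12, W14 and W16, which is 106 − 78 = 28 days, because a first failing value at W20 gives 134 − 78 = 56 days and satisfies the relapse criterion. Missed Hb visits loosen this further, since relapse counts only at a measured value.

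**2. When a transfusion is enough, without noise.** Assume a transfusion 2 days before the opening visit, an immediate rise U, and linear loss over L days. None of these values is in the documents. For a W12 opening the last value needed is at W16, 30 days after the transfusion:

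change at W16 = underlying change + U × (1 − 30/L)

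- Underlying 0, U = 2, L = 112: 2 × 0.732 = 1.46, fails. U = 3, L = 84: 3 × 0.643 = 1.93, passes.
- Underlying +0.5, U = 2, L = 84: 0.5 + 1.29 = 1.79, passes.
- Underlying +1.0, U = 1, L = 84: 1.0 + 0.64 = 1.64, passes.
- Underlying −0.5, U = 3, L = 112: 2.20 − 0.5 = 1.70, passes. In the grid checked (U = 1, 1.5, 2, 3; L = 56, 84, 112), this is the only passing case at −0.5.
- Underlying −1.0, U = 3, L = 112: 2.20 − 1.0 = 1.20, fails, as does every other case at −1.0.

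For most other openings the last value needed is 44 days after the transfusion. With no underlying change, U = 3 then passes at L = 112 (3 × 0.607 = 1.82) but not at L = 84 (3 × 0.476 = 1.43).

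A transfusion can also start the clock early for a short real rise. A true +1.6 g/dL seen only at W14 and W16 fails alone (134 − 92 = 42 days). It qualifies if a transfusion with U = 2, L = 84 comes just before W10 or W12.

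**3. With noise and visit variation.** Observed change = δ + u × g × (1 − t/L) + noise − baseline error. Here δ is the underlying change, u the units, g the rise per unit, t the days since transfusion (donor effect zero once t reaches L), and the baseline error is that of a mean of two values. Assumptions, not in the documents: g = 0.8-1.0 g/dL, L = 100-120 days, within-patient Hb SD 0.3-0.5 g/dL, ±3-day visits, one transfusion on a random day from 2 to 104. Ranges run over all combinations, and all are conditional on that transfusion.

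| Underlying change | Untransfused | 2 units | 3 units |
|---|---|---|---|
| 0 | about 0% | 1-12% | 12-61% |
| +0.3 g/dL | about 0% | 6-31% | 33-82% |
| −0.5 g/dL | about 0% | 0-2% | 1-20% |

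At −1.0 g/dL, the 2-unit figure is 0-0.1%.

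**4. Effect of an exclusion window (2 units, no underlying change).** A 7-day window leaves up to about 8-9%; a 28-day window leaves at most about 2%.

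**5. What it could do to the protocol's test.** The exact binomial with N = 45 and null 0.20 rejects at 15 or more responders (alpha 0.02499). Power at 0.40 is 85.7%, 1.6 points below the stated 87.3%, which does not affect this point. With 15 NTD patients and a true rate of 20% in all strata, add an average of k false NTD responders, so that the NTD rate is 0.20 + k/15 and the other 30 patients stay at 0.20. The rejection probability becomes 0.057, 0.112 and 0.192 for k = 1, 2 and 3. The value of k is purely illustrative.

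**The case against.** The strongest reply is that the relapse criterion already does most of the work. Every measured Hb must hold at or above +1.5 g/dL until at least 8 weeks after the first. Two units the day before W12 must still give 1.5 g/dL at W16, 29 days later; without noise the four corner combinations in step 3 give 1.14, 1.21, 1.42 and 1.52, so only the most favourable passes. Three units at once exceeds the most an NTD patient may have received in the whole 16 weeks before entry. These points stand. They make the 3-unit column an upper case and place the main risk in patients with some underlying rise.

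A reader might infer that treatment failure itself manufactures responders. The calculation does not support that: in patients who truly worsen the effect is small after 2 units and nearly vanishes at −1.0 g/dL.

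A reader might also infer that the SAP loosened the endpoint. It did not; the protocol has the same gap. Nor can the rejection probabilities in step 5 be read as the trial's error rate. No NTD transfusion rate is given, and SAP 4.2.1.1 specifies proportions without a test against 20%, which appears only in the protocol.

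Finally, transfusions and Hb will all be listed (SAP 3.2), so an affected responder could be found by hand. That helps a careful reader of the listings but does not correct the reported proportion.

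**Conclusion.** The gap is real. As written, the rule can count transfusion-raised Hb as erythroid response in the NTD stratum, and the bias runs only toward benefit. The realistic route is a transfusion that pushes a stable or partly improved Hb over the threshold, or that opens the interval early for a short rise. The probabilities rest on assumed rise per unit, rate of loss and Hb variability, and on a transfusion having occurred, so the expected number of false responders cannot be stated. This is a worthwhile refinement of the endpoint derivation, not a contradiction between the documents.

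**What to change.** Analysis rule only; nothing changes in patient care. In SAP 4.2.1.1 (NTD), add: *An Hb value obtained within a stated period after any RBC transfusion cannot start or support a qualifying interval.* Set the period to at least the 7 days that the protocol already applies to entry Hb.

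Because 7 days removes only part of the bias, add a sensitivity analysis with a longer window, such as 28 days. That length rests on assumed kinetics and appears in neither document, so it should be labelled as a choice. Flag in the primary table or listing any NTD responder who was transfused on study before the response began.

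The cost is one sentence and one derivation. Protocol 8.2.2 already collects transfusion dates and units. The small downside is that a true response beginning soon after a transfusion is dated later and may miss Week 24.
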